### **13.3 Study Monitoring**

The Sponsor of this clinical investigation will be responsible for monitoring this study. The monitor's duties are to aid the Investigator in the production and maintenance of complete, legible, well-organised and easily retrievable data. In addition, the Monitor will be responsible for assuring the Investigator understands the CIP and all applicable regulations. Approaches to monitoring may include both remote and on-site visits as appropriate and the rationale and frequency for monitoring will be at the Sponsor's discretion.

The Monitor may check the eCRF entries with source documents. In order to perform this role effectively, the Monitor must be given access to primary subject data which supports the information recorded on the eCRF, i.e. hospital notes, appointment books, original laboratory records, etc. Access to these documents must also be given should the regulatory authority instigate an external audit. Since a subject has the right to refuse access to these documents on the grounds of confidentiality, consent to access is included in the informed consent document, which the subject signs.

The Sponsor will be responsible for establishing the schedule and procedures to be followed for monitoring this clinical investigation and may also include the monitoring of the operative procedure. The Investigator will receive reasonable notification prior to each monitoring visit during the course of this clinical investigation. At each visit, the Investigator will be expected to co-operate with the Monitor for the review and verification of eCRFs and any additional records as may have been previously arranged between the Investigator and the Monitor.

The monitoring frequency will be determined by the Sponsor for each Site based on factors including: the planned enrolment, the rate of enrolment, the level of experience of the clinical investigation team and the current study conduct. Study conduct can be evaluated remotely based on compliance percentage, discrepancy rate and discrepancy type. In general, the source data verification will be performed on a random sample of subject records. In order to perform this role effectively, the Monitor must be given access to primary subject data which supports the information recorded on the CRF, *i.e.* appointment books, original laboratory records, etc. Consent to access this information is included in the patient consent form, which the Subject signs.

#### **13.4 CIP Amendments**

If it becomes necessary to amend the Clinical Investigation Plan, the nature of the amendment may be discussed, if required, between the Sponsor and the Lead Investigator. Protocol amendments will be submitted to the appropriate Ethics Committee(s) for review and approval if required, before they are implemented.

#### **13.5 Product Labelling**

Refer to Exhibit C for Product Labelling.

#### **13.6 Sponsor Study Termination**

The Sponsor may prematurely terminate or suspend the clinical study as a whole or at an individual investigational site for significant and documented reasons. Reasons for premature termination or suspension include, but are not limited to safety, inadequate recruitment, Investigator issues, device related problems, alignment with business strategy or administrative issues.

If suspicion of an unacceptable risk to subjects arises during the clinical study, or when instructed by an Ethics Committee or Regulatory Authority, the Sponsor shall suspend the clinical study at all active sites while the risk is assessed. The Sponsor shall terminate the clinical study if an unacceptable risk is confirmed, or resume the clinical study following appropriate communication and approval from the Ethics Committee and Regulatory Authority as required.

In terminating the clinical study, the Sponsor and the Investigator will assure that adequate consideration is given to the protection of the subject's interests per Section 11 and all documentation is archived per Section 12 and the appropriate bodies such as the Ethics Committees and Regulatory Authorities are informed as appropriate.

### 13.7 Insurance

The Sponsor recognizes its liability in law to compensate for any injury sustained by a subject participating in this clinical investigation as a result of negligence or breach of duty of care; adequate insurance provisions have been made by DePuy Synthes Joint Reconstruction to compensate any Subject so injured.

### 13.8 Financial Agreement

Funding of this clinical investigation will be the subject of a separate agreement between the Sponsor and the Institution where the clinical investigation is being conducted and the Principal Investigator (where permitted by the Institution).

## 14. PUBLICATION PLAN

All manuscripts of data obtained from this clinical investigation will be reviewed and approved by the Sponsor, and each author, prior to any submission. The current and applicable J&J Publication Policy will be followed.

DePuy Synthes will require a written agreement for any external author(s) prior to initiating any publication. All authors must disclose financial or personal affiliations that could be considered a conflict of interest.

## 15. EXHIBITS

Exhibit
A. Surgical Technique
B. Radiographic Protocol
C. Instructions For Use

- Appendix: Tables, Listings and Graph Shells

List of Abbreviations

AE	Adverse Event
BMI	Body Mass Index
CIP	Clinical Investigational Plan
n	Non-missing data
PG	Performance Goal
PMCF	Post Market Clinical Follow-Up
SAP	Statistical Analysis Plan
SD	Standard Deviation

1. Study Design

This study is designed as a prospective, multi-centre, non-comparative, uncontrolled Post Market Clinical Follow-Up (PMCF) Study.

There will be 157 patients with the GLOBAL ICON Stemless Shoulder System in Total Shoulder Arthroplasty in up to 20 sites located in the United Kingdom, the Netherlands, Germany and Canada. A maximum of 30 subjects may be recruited from one site. More than one implanting surgeon may recruit subjects at each site. A complete description of the methods for determining sample size is contained in Section 7.

Patients will be followed after surgery at several times: immediate Post-Op, 3-, 12-, 24-, 60- and 120-months. The data up to and including 24-month follow-up visit will be used to determine the effectiveness and safety of the device. The primary, safety, secondary and tertiary objectives are presented below.

1.1 Primary Objective

The primary objective is to evaluate success of the device at the 24 month visit following implantation. Success is a composite outcome that includes both effectiveness and safety endpoints and will be established if all of the following conditions are met at the 24 month visit: 1) radiographs indicate that there is no continuous radiolucent line (RLL) around the humeral component, with a continuous RLL defined as a radiolucent line $> 1\text{mm}$ in all five zones of both the AP and Axillary views, and 2) the adjusted Constant-Murley score is greater than 85, and 3) the Global ICON humeral component has not been removed for any reason, and 4) there has been no device-related serious adverse events.

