### **3.4 Study Objective and Endpoints**

#### **3.4.1 Primary Objective and Endpoint**

The primary objective of this PMCF study is to confirm device survivorship of the GLOBAL ICON stemless humeral component at 24 months post-operative.

The primary endpoint in this study is composite success at 24 months if each of the following criteria is met:

- Radiographs indicate that there is no continuous radiolucent line (RLL) around the GLOBAL ICON stemless humeral component, with continuous RLL defined as a radiolucent line > 1mm in all five zones of either AP or Axillary views
- The adjusted Constant-Murley score is greater than 85, with the adjustment based on the method of Constant
- No GLOBAL ICON humeral component has been removed for any reason
- There have been no device-related serious adverse events

---

 Katolik, Leonid I., Romeo, Anthony A., Cole, Brian J., Verma, Nikhil N., Hayden, Jennifer K., Bach, Bernard R. Normalization of the Constant Score. Journal of Shoulder and Elbow Surgery 2005; 14:279-285.

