## 5.5 Radiographic Assessments

All radiographs will be submitted to an imaging vendor, Medical Metrics Inc. (MMI) for review and evaluation. MMI will complete eCRFs to document the radiographic findings under the scope of the study specific Radiographic Evaluation Protocol (Exhibit B).

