### 7.5 Handling of Missing Data for the Primary Endpoint

For analysis of the primary endpoint, subjects who withdraw prior to the 24-Month Interval will be included in the analysis as composite endpoint failures if they had one of the following events either intra-operatively or post-operatively:

- A post-operative radiograph indicated a continuous radiolucent line (RLL) around the humeral prosthesis, with continuous RLL defined as a radiolucent line > 1mm in all five zones of either AP or Axillary views
- A revision occurred in which a GLOBAL ICON humeral component was removed
- The subject had a device-related serious adverse event (SADE)

Participants who withdraw prior to 24-month follow-up and did not experience any of the clinical outcomes listed above will be considered to have missing values on the clinical outcomes/primary endpoint, which will be addressed through multiple imputation methods (see SAP for further details).

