#### **7.10 Interim Analysis**

There are no planned interim analyses for the purpose of stopping the study early. An interim analysis is planned to support a US marketing application, which will include demographic summaries, the primary endpoint analysis, a Kaplan-Meier analysis of device survivorship, and summaries of safety

outcomes. Additional ad-hoc analyses may be performed to support conference presentations or abstracts prior to the end of the study.

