9.4 Hypothesis Testing of Primary Endpoint

The primary endpoint analysis will seek to demonstrate that at the 24 month visit after surgery, the composite success (p), which is based on four study outcomes (radiograph demonstrating no continuous radiolucent line around the humeral component, adjusted Constant-Murley Score > 85, no removal of the humeral component, no serious adverse events related to the device), is significantly greater than a performance goal (PG) of 75%. The null and alternative hypotheses for this endpoint are as follows:

Null hypothesis H_{01} : $p \leq 75\%$

Alternative hypothesis H_{A1} : $p > 75\%$

The null hypothesis will be rejected and the alternative hypothesis will be accepted if the lower bound of a two-sided 95% confidence interval is greater than 75%. The performance goal of 75% used in the hypothesis test described above is based on the percentage of successful stemmed implants at the 24 month visit reported elsewhere using a similar definition of success [4]. Therefore, the hypothesis test implies a comparison to performance of stemmed implants. In a prior study, non-inferiority of the Simpliciti stemless humeral device to stemmed devices was demonstrated using a PG of 65% (75%-10% non-inferiority margin) [4]. Therefore, the current study sets a higher bar to establish successful performance of Global Icon when compared to the study evaluating the Simpliciti device.

Another objective using the same endpoint is to establish non-inferiority of Global Icon to Simpliciti conditional on rejection of H_{01} . To do so a PG or non-inferiority margin of 78.74% (Simpliciti success percentage of 88.74% [5] -10%) is selected. The null and alternative hypotheses for this objective are as follows:

Null hypothesis H_{02} : $p \leq 78.74\%$

Alternative hypothesis H_{A2} : $p > 78.74\%$

The null hypothesis will be rejected and the alternative hypothesis will be accepted if the lower bound of a two-sided 95% confidence interval is greater than 78.74%. Notably,

simultaneous testing of these nested null hypotheses (H_{01}, H_{02}) does not inflate the Type I error rate [6,7].

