9.8 Missing Data

9.8.1 Primary endpoint

As detailed in the CIP, participants who withdraw prior to the 24-month follow-up visit (i.e., lost to follow-up) and did not experience a continuous RLL around the humeral component, a serious adverse device-related event or a revision surgery in which the humeral component was removed, would have missing data on their clinical outcomes, which will be addressed using imputation. Imputed values will be used to determine whether patients who withdraw prior to the 24-month follow-up visit are categorized as successes or failures on the primary endpoint. Specifically, determining success or failure on the primary endpoint for each patient withdrawing prior to the 24-month follow-up visit will be based on imputed values of clinical outcomes that make up the primary endpoint. Patients will be scored as a failure on the primary endpoint if their imputed values indicate continuous RLL around the humeral prosthesis or a revision in which the humeral component was removed or a SADE took place or the adjusted Constant-Murley score ≤ 85.

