9.8.5 Imputation Model

A single imputation model will be used to impute values for the primary, secondary and tertiary endpoints (not including survival endpoints). The variables used to define the primary endpoint are presence/absence of a: continuous RLL around the humeral component, a serious adverse device-related event, revision surgery of the humeral component and the adjusted Constant-Murley score. For the adjusted Constant-Murley score, we will create separate variables for scores obtained at each assessment to include in the imputation model. For the other variables that make up the primary endpoint, partitioning by time could produce computational problems, therefore we will consider a model in which the presence/absence of the outcomes will be imputed irrespective of their timing. Even with this simplification, computational problems may arise for various reasons, such as no events for one of the clinical outcomes or severe multicollinearity. In

these cases, we will document the problem and fit a further simplified imputation model that pools one or more of these clinical outcomes together. Another potential modification to the imputation model is the use of individual items rather than total adjusted Constant-Murley score if for some patients there were missing items for a particular assessment.

Incorporating additional variables in the imputation model served two objectives. First, they can improve prediction of clinical outcomes used to construct the primary endpoint. Second, they can be used to address missing data on the secondary and tertiary endpoints. Among the variables included in the imputation model to support these objectives are the Oxford Shoulder score, EQ-5D-5L summary score and demographic variables (age, gender BMI and primary diagnoses). For the Oxford Shoulder score and EQ-5D-5L summary score separate variables for scores obtained at each assessment will be created and included in the imputation model.

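### The SAP counts a continuous radiolucent line as a failure only if it is complete in both views, the protocol if it is complete in either, and nothing in the two documents reconciles them

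*SAP*

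**What the plan says.** - SAP 1.1 makes a subject a success only if, among other things, the radiographs show no continuous RLL. It defines that as a line over 1 mm "in all five zones of both the AP and Axillary views".
- Protocol 3.4.1 lists the same criterion, "with continuous RLL defined as a radiolucent line > 1mm in all five zones of either AP or Axillary views".
- Protocol 7.5, which decides which withdrawals count as failures, repeats the protocol rule: "defined as a radiolucent line > 1mm in all five zones of either AP or Axillary views".
- SAP 9.8.1 handles withdrawals by reference to the protocol ("As detailed in the CIP, participants who withdraw prior to the 24-month follow-up visit") and does not restate a view rule.
- The remaining statements name a continuous RLL without saying how the views combine: the protocol synopsis, protocol 7.6 and 7.9.1, SAP 9.4 ("radiograph demonstrating no continuous radiolucent line around the humeral component") and the imputation variable in SAP 9.8.5 ("presence/absence of a: continuous RLL around the humeral component").
- Protocol 5.5 has the imaging vendor record radiographic findings under Exhibit B, which is not among the documents available for review.

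**The concern.** The two rules differ for any subject with a complete line in exactly one view, and they differ on a component of the only endpoint that is powered. That endpoint is tested against 75% and then, under SAP 9.4, against 78.74%. Protocol 7.10 also puts it to use outside the study: "An interim analysis is planned to support a US marketing application, which will include demographic summaries, the primary endpoint analysis". Analysts working from the two documents could report different primary results from the same films, or the rule could be settled after the results are known.

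The conflict can also arise inside one analysis. SAP 1.1 scores the 24-month visit by *both*. SAP 9.8.1 sends the reader to the protocol for withdrawals, and the protocol says *either*. Read literally, completers and withdrawals would be scored by different rules, and the single RLL variable in the imputation model would have no settled coding.

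**Working it through.** **1. The plan's own figures.** Inputs from protocol 7.8 and SAP 8: null 75%, assumed success 85%, one-sided alpha 0.025, power above 80%, 15% attrition. The exact binomial test at n = 133 needs 110 successes, with attained alpha 0.0223 and power 80.8%. The smallest n above 80% power comes out at 132 (81.8%), one below the stated 133. 133 / 0.85 = 156.5, rounded up to 157. None of these inputs depends on the view rule, so the conflict leaves the sample size unchanged.

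**2. The two rules side by side.**

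| Complete line (>1 mm, all five zones) in | Protocol 3.4.1 and 7.5 | SAP 1.1 |
|---|---|---|
| neither view | passes | passes |
| AP only | fails | passes |
| axillary only | fails | passes |
| both views | fails | fails |

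Failures under *both* are a subset of failures under *either*. Moving from the protocol rule to the SAP rule therefore leaves the composite success count equal or higher, never lower. A subject with only one readable view can be shown to fail under *either* but not under *both*. Protocol 5.3.2 requires only the AP view immediately after surgery, so a withdrawal whose only film is from that visit is in this position.

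**3. Effect of one reclassified subject.** Take n = 157, all observed. The lower bound uses the normal approximation named in SAP 9.5: x/n − 1.96 × √[(x/n)(1 − x/n)/n].

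| Successes | Rate | Standard error | Lower 95% bound |
|---|---|---|---|
| 127 | 80.89% | 3.14% | 74.74% |
| 128 | 81.53% | 3.10% | 75.46% |
| 132 | 84.08% | 2.92% | 78.35% |
| 133 | 84.71% | 2.87% | 79.08% |

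The thresholds are 128/157 for the 75% goal and 133/157 for the 78.74% goal. One subject moves the rate by 1/157 = 0.64 point and the bound by about 0.7 point.

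**4. How often one subject would decide the test.** This needs a protocol-rule count exactly one below the threshold. With X binomial(157, 0.85), P(X = 127) = 3.1% and P(X = 132) = 8.2%. If 133 subjects are analysed without imputation, the thresholds are 109 and 113, and P(X = 108) = 4.4% and P(X = 112) = 9.2%.

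**5. Illustration with an assumed discordance.** Let d be the share of subjects with a complete line in exactly one view who meet the other three criteria. The documents give no value for d. Put true protocol-defined success exactly at the goal, score by the SAP rule, and compute P(X ≥ threshold) for X binomial(157, goal + d).

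| Goal | d = 0 | d = 1/157 | d = 1 point |
|---|---|---|---|
| 75% (128 needed) | 3.3% | 4.9% | 6.0% |
| 78.74% (133 needed) | 3.8% | 5.6% | 7.0% |

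The excess over 2.5% in the d = 0 column comes from the normal approximation, not from the RLL rule. The other columns are not the type I error of either rule applied consistently. They describe truth set by one document and scored by the other.

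**The case against.** The strongest reply is about weight. A subject matters only with a line over 1 mm in all five zones of exactly one view, an adjusted Constant-Murley score above 85, no component removal and no device-related serious event. That combination may never occur. This stands: no effect on the result has been shown, and the d-based figures are illustrations only.

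Second, the reference to the protocol in SAP 9.8.1 can be read as a sign that the SAP means to follow the protocol throughout, which would make SAP 1.1 a transcription slip. That is plausible, and mixed scoring of completers and withdrawals is a possible reading rather than a stated plan. But where the plan deliberately changed a method, from the exact test to the Z-test, both documents carry a note saying so. The RLL rule has none, and SAP 1.1 as it stands is an explicit instruction to the analyst.

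Third, Exhibit B or the separate table shells may fix how the RLL variable is derived. They might, and the statement that nothing reconciles the rules extends only to the protocol and SAP. If they do contain a rule, one of these two texts would still be wrong.

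Fourth, the figures in step 4 leave out attrition and the planned multiple imputation. The 133-subject variant shows that allowing for attrition alone changes them little. Rubin's variance is not modelled in either version.

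**Conclusion.** The contradiction is real, and the SAP's version is the more lenient. The practical effect cannot be determined from the documents and may be nil. Per reclassified subject it is 0.64 point on the success rate and about 0.7 point on the lower bound. A single such subject would be decisive with probability 3.1% (75% goal) or 8.2% (78.74% goal), assuming 85% protocol-rule success, 157 observed subjects and no imputation.

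It must be fixed all the same. That judgement rests on the need for one definition of the only powered endpoint, fixed before it is analysed, and not on a demonstrated change in the result.

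**What to change.** Before any run of the primary analysis, including the one in protocol 7.10:

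1. Settle on one rule. By default, correct SAP 1.1 to the protocol's *either*, which the protocol states in both places where it gives a view rule.
2. Apply it uniformly to subjects assessed at 24 months, to withdrawals (protocol 7.5, SAP 9.8.1) and to the RLL variable in the imputation model (SAP 9.8.5). State it, or cross-refer to it, in SAP 9.4.
3. If *both* is what the sponsor intends, amend protocol 3.4.1 and 7.5 with a rationale, and report the primary result under the present *either* rule as a sensitivity analysis.
4. Check the chosen rule against Exhibit B and the table shells, including how a missing or unreadable view at 24 months is scored.

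The default costs a wording correction and a document check. The sample size does not change. The observed success rate may be slightly lower than under the present SAP wording, or identical if no subject has a complete line in exactly one view.

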1.2 Safety Objective

The safety objective is to evaluate the overall survivorship of the device as well as to characterize adverse events. For overall survivorship, a device is deemed to be surviving if no components have been removed for any reason. Survival is based on Kaplan-Meier methodology, with survival reported at the last day of the 24-, 60- and 120-months post-operative assessment window (see section 4). For adverse events (AE), the type and

frequency of all AEs in this study will be summarized, with distinction of serious AEs, operative and device related AEs.

